Provide a clear, concise narrative of study procedures with special attention to the subjects' involvement. Detail the overall study timeline and location of study procedures, list all interventions, assessments and interviews, estimate the duration of each procedure, provide dosing schedules, identify study personnel involved in each procedure, and provide credentials for relevant personnel. For complicated study designs, we strongly encourage attaching tables, flow-charts, and study algorithms.

In the R61, we will confirm target engagement of D-serine + auditory remediation, assess relationships of plasticity changes and cognition, safety and assess the optimal dose of D-serine treatment. In the R33, we conduct a randomized, placebo-controlled, parallel group study with the superior dose of D-serine combined with 16 weekly sessions of the same neuroplasticity-based auditory remediation. The structure of this grant requires successful completion of the R61 phase over 2 years prior to initiation of the R33 phase. We will amend the PSF and consent to include a full description of the R33 phase prior to its initiation.

The study will be conducted in groups of 15 subjects in which 12 subjects will receive D-serine for each of the three treatment visits and 3 will receive placebo for each of the three treatment visits. The first group of 15, will receive 80 mg/kg or placebo, and the second group of 15 subjects will receive 100 mg/kg or placebo, followed by a third group receiving 120 mg/kg or placebo. As previous studies noted minimal carry over effect of D-serine effects ([name] 2010), subjects may be permitted to participate in more than one phase with at least a six

month space in between.

If there are tolerability concerns at the 80 or 100 mg/kg doses, we will add a 60 mg/kg arm, ensuring the assessment of multiple doses. After each cohort, we will obtain permission from both the FDA and the IRB via an amendment, prior to the beginning of the next cohort. We require this safety milestone to be reached in order to begin the next cohort.

R61 Design (Table 1):

R61 Design	Table 1 (R61)	Baseline	Treatment Day			Follow-up ¹
			1	2	3	
		Day -30 to -1	Day 1	Day 8±2	Day 15±2	
	Consent	x				
	Medical screening	x				
	D-serine/Placebo		x	x	x	
	MMN		x	x	x	
	Auditory Remediation/EEG		x	x	x	
	Cognitive and behavioral ratings	x				
	Clinical laboratory/pregnancy/vitals	x	x	x	x	x
	SAFTEE/C-SSRS	x	x	x	x	x
	1. If necessary to follow-up any abnormalities.					

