Screening/Informed consent: Informed consent will be obtained before any study procedures, including screening procedures, are initiated. After providing informed consent, subjects will undergo full medical screening (medical history, physical examination, vital signs, laboratories for basic chemistries, blood counts, liver function tests, urinalysis, urine toxicology, serum pregnancy test for women, and thyroid tests, electrocardiogram [EKG]) and psychiatric screening (i.e., Structured Clinical Interview for DSM V Axis I Disorders (SCID) to confirm eligibility. Screening will occur over an up to 31-day screening period.

Baseline ratings: Eligible subjects will then undergo baseline cognitive and behavioral tests:

Randomization: Assignment to treatment groups will be on a random basis. Randomization will be stratified by baseline tone matching.

Auditory remediation visits: Subjects will then undergo three auditory remediation/EEG sessions. Each visit will follow the same format. Sessions are administered once a week±2 days. We utilize an auditory remediation program, in which participants are presented with paired tones (e.g. Stimulus 1 (“reference”) and Stimulus 2 (“test”): S1 and S2) and indicate which tone is higher in pitch (frequency). In the first pair, the ratio is 50% (e.g. 1000±500 Hz), and the difficulty level is adjusted to maintain a steady (~70% correct) level of performance across the 80 repeats. Ratios in each pair are log-transformed and averaged across 10-trial pairs (e.g., pairs 1-10, 11-20, etc.). When the reference (S1) remains constant (“fixed”), highly significant improvement is seen.

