After a negative urine pregnancy test for fecund women and the Columbia Suicide Severity Rating Scale (C-SSRS), each visit will begin with a pretreatment EEG/capping. Subjects will then receive D-serine or placebo. Auditory remediation will begin 30 minutes after study drug administration, to allow for training during peak D-serine levels ([name], Malhotra et al. 2010). EEG will be recorded during sessions, to assess theta-ITC and secondary EEG measures. Immediately after auditory remediation, subjects will complete post treatment MMN. A D-serine level will be drawn immediately after the session using established methods to allow for functional pharmacodynamics readout, along with urinalysis and clinical laboratory assessments. The SAFTEE will be used to assess general side effects. Columbia/NKI EEG labs are both under the supervision of Drs. [name] and [name] and have previously conducted parallel studies, ensuring cross-site validation.

Study drug and maintenance of the blind: D-Serine and placebo will be administered as a solution, prepared (premixed) in water and prescribed only as “study medication.” D-serine will be dosed by weight (e.g. 80 mg/kg

for the 1st cohort). Study medication will be dispensed to subjects in individual, identical appearing bottles, and dispensed on the day of the session by an un-blinded pharmacist otherwise uninvolved in the study. As previously, D-serine will be obtained from Evonik, and an artificial sweetener will be used as placebo.

The un-blinded pharmacist, based upon predetermined assignment schedule, will make study assignment. Envelopes containing treatment assignment will be kept in pharmacy and in patients' clinical charts. Envelopes will be unsealed only in cases of medical necessity. Blind-breaks will be on individual subject basis only. The pharmacist does not participate in assessing any dependent variable and conveys no information about drug status to patients or staff except in a medical emergency.

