For treatment studies: To minimize risks to subjects, operationalized drop-out criteria should be defined so that subjects who worsen, or in some cases, fail to improve, are removed from the study and offered standard care. The threshold for drop-out should consider the level of risk associated with non-improvement for the specific disorder, the availability of alternatives, and the typical required duration of treatment. For example, emergence of suicidal intent, or psychosis, should prompt immediate clinical evaluation and withdrawal from the study.

The following safety procedures will be followed, as approved under our IND.

- Urinalysis with microscopics will be done at every visit.
- Immediately discontinue D-serine for unexplained serum creatinine increase >0.3 mg/dL over the pre-study value or for >1 granular or muddy casts. Treat as serious adverse event (SAE) possibly related to study medication. Repeat until clear x 2 to demonstrate reversibility
- Hold D-serine for >1 hyaline casts, and repeat lab. Ask subject to eat more salt and drink more water. If absent on repeat, reinstate D-serine and treat as adverse event (AE). If present on repeat, continue to hold d-serine and repeat lab once again. If still present on second repeat, discontinue D-serine and treat as SAE possibly related to study medication. Repeat until clear x 2 to demonstrate reversibility.
- Hold D-serine for proteinuria > 100 mg/dl or unexplained glucose >250 g/dl (both equivalent to 2+). If absent on repeat, resume D-serine and treat as AE. If still present on repeat, discontinue D-serine. Repeat until clear x 2 to demonstrate reversibility. This would be treated as SAE possibly related to study medication. Unexplained glycosuria is defined as increased urine glucose in absence of corresponding increase in serum glucose levels, in patients without glycosuria at baseline.
- Continue D-serine for proteinuria >30 but <100 mg/dl (1+), or unexplained glycosuria (>100 but < 250 g/dl) but repeat. If absent on repeat, continue D-serine and treat as AE. If still present on repeat, hold D-serine and repeat

once more. If absent on repeat, resume D-serine and treat as AE. If still present on second repeat, discontinue D-serine and treat as SAE possibly related to study medication. Repeat until clear x 2 to demonstrate reversibility.

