The PI has an active IND for D-serine (122821), specifically permitting use up to 120 mg/kg in this protocol.

D-serine is a naturally occurring amino acid that is present in high concentrations in the human brain. D-serine is cleared almost exclusively by the kidney.

The primary safety concern of D-serine is the potential for nephrotoxicity. Nephrotoxicity is a theoretical concern during D-serine treatment, as rats receiving D-serine experience a reversible acute tubular necrosis. When present, this toxicity leads to high levels of glucose and protein being present in the urine. This effect, however appears to be isolated to rats, in that other rodent species (e.g., mice) do not show similar sensitivity to D-serine, nor is toxicity observed in non-rodent species (e.g., rabbit, dog, monkey)²¹⁹. Further, toxic effects of D-serine, even in rats, are fully reversible even with continued D-serine treatment. The specific sensitivity of rats appears to be due to the presence of a D-serine transporter in rat kidney that actively reabsorbs D-serine from the urine, leading to buildup of high levels within the rat kidney. The presence of this transport mechanism is apparent from the low levels of D-serine in rat urine relative to that of other species, despite relatively similar serum levels.

In humans, there is no evidence of reabsorption of D-serine by the kidney. The safety of high dose D-serine in non-rat animal species has been further established as part of the safety reports provided to the FDA for my IND.

14 human trials have been published with D-serine (Table), including 431 subjects and treatment duration up to 16 weeks of daily dosing. 102 subjects received high dose (>30 mg/kg), including 16 patients at 120 mg/kg. Across all of the studies, only one subject was reported to have abnormal renal values related to D-serine treatment. The abnormality occurred in a subject receiving 4 weeks of the 120 mg/kg dose. Even at that dose, the abnormality was extremely mild in that it involved only an increase in protein (2+ by dipstick) without accompanying increase in glycosuria or change in creatinine level. The abnormal urinalysis values were observed 4 weeks following treatment onset, and fully resolved within a few days of stopping treatment.

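### Renal labs at each treatment visit follow that day's dose, so both weekly re-doses are given without a routine renal result from later than a few hours after the previous dose

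*Protocol*

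**What the plan says.** Under *Auditory remediation visits* in *Study Procedures*, the Protocol sets one format for all three treatment visits. "After a negative urine pregnancy test for fecund women" and a suicide rating, "each visit will begin with a pretreatment EEG/capping. Subjects will then receive D-serine or placebo". Remediation starts 30 minutes after the dose, with EEG running, and MMN follows. Then a D-serine level is "drawn immediately after the session using established methods to allow for functional pharmacodynamics readout, along with urinalysis and clinical laboratory assessments". On spacing: "Sessions are administered once a week±2 days".

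The *Dose escalation plan* likewise places renal monitoring after each dose. Table 1 and *Criteria for Early Discontinuation* call for laboratory tests and urinalysis at every visit, but neither says at what point in the day. The Follow-up column of Table 1 is conditional: "If necessary to follow-up any abnormalities".

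*Criteria for Early Discontinuation* holds the drug for 2+ protein or unexplained 2+ glucose and asks for a repeat. For 1+ readings the drug continues while the test is repeated, and is held only if the repeat is still positive. No time limit is set for any repeat.

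The Protocol names kidney toxicity as its main safety concern. Of the rat finding behind that concern, *Risks associated with D-serine* says "this toxicity leads to high levels of glucose and protein being present in the urine".

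**The concern.** A hold rule protects a subject only if the result it acts on is in hand before the next dose. Under the written visit order, the renal information available at a re-dose comes from a sample taken a few hours after the previous dose. The Day 8 and Day 15 samples could reveal an effect that developed later and persisted, but they are taken after that day's dose. Such a subject would be dosed on top of the effect, and the hold would come one dose late.

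The rule for 1+ readings has a related gap. Because the repeat has no deadline, a site could use the next scheduled sample as the repeat, and that sample also follows another dose.

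**Working it through.** The plan states no dose-to-sample time, so there is no figure to reproduce. The check derives the time from the visit steps and then counts the decisions affected.

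**Inputs**
- Wait from dose to remediation: 0.5 h (*Auditory remediation visits*).
- Electrophysiology: 2–3 h (*Assessment Instruments*). EEG runs during remediation and MMN follows it, so the post-dose activity is electrophysiology. Part of the block may be pre-dose capping.
- Spacing: 7 ± 2 days.
- Allocation: 12 active and 3 placebo in each of three cohorts, three doses each (*Study Procedures*).

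**1. Dose-to-sample time (inferred)**
- Whole block after the wait: 0.5 + 2 = 2.5 h to 0.5 + 3 = 3.5 h.
- Block includes the wait and 0.5–1 h of pre-dose capping (assumed): 2 − 1 = 1 h to 3 − 0.5 = 2.5 h.
- Remediation counted separately at 1 h (assumed from 16 hours over 16 sessions in the R33 description, *Lay Summary*): 0.5 + 1 + 3 = 4.5 h. This fits poorly with EEG being recorded during remediation.

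The range is about 1–4.5 h. As a share of a 168 h week, 4.5/168 = 2.7% and 1/168 = 0.6%.

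**2. Time to the next routine renal sample**

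The next dose comes 5–9 days later (120–216 h), and that visit's sample follows it. If the Day 8 ± 2 and Day 15 ± 2 windows in Table 1 are read as independent, the second interval could be 13 − 10 = 3 to 17 − 6 = 11 days. On any of these readings, no routine result falls between the in-session sample and the re-dose.

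**3. Decisions affected**
- Active subjects: 3 × 12 = 36. Active re-doses: 36 × 2 = 72.
- With placebo: 45 × 2 = 90 re-doses.
- Third active doses with no later routine sample: 36.

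**4. What a test on arrival could add**

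A marker that starts at time *s* after a dose is visible on arrival only if it lasts at least (gap − *s*). For *s* = 1 day (an illustration; the documents give no onset time), it must last 5 − 1 = 4 days at the shortest spacing, 7 − 1 = 6 at the usual spacing and 9 − 1 = 8 at the longest. The arrival test therefore helps with persistent effects only.

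**The case against.** **Prior experience is reassuring.** The Protocol's safety table lists 21 patients on weekly 60 mg/kg with no renal abnormality. In the daily-dosing trials (up to 16 weeks; 16 patients at 120 mg/kg for 4 weeks), subjects were re-dosed every day, so samples after the first days followed earlier doses by a day or more. One abnormality is reported: 2+ protein without a creatinine change, which cleared within days of stopping. Weekly dosing gives one seventh of the daily exposure. This stands, and it is why the likelihood is probably low. The limit is that weekly dosing above 60 mg/kg is new here, and the one case arose at the dose planned for cohort 3.

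**Regulators accepted the monitoring.** The hold rules and post-dose sampling are part of the IND, and fuller safety and pharmacokinetic detail is in a grant application not available here. This also stands: a time course missing from these documents may exist elsewhere. It does not alter the visit order as written, and the proposal keeps every existing sample.

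**Holding for 1+ protein on arrival would contradict the continue rule.** This is a fair point, so the fix has to say how the two fit together. It does so by timing the repeat and leaving the thresholds alone.

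**Stronger readings.** A reader might infer that renal harm is being missed, or try to put a figure on the share of effects that would go undetected. The documents support neither. They give no onset or duration for a renal effect of a single dose, so any such share would depend entirely on the times assumed. Nor is re-dosing unguarded: an abnormal in-session result triggers the hold rules, and Day 8 and Day 15 samples do look for persisting effects, only late.

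**Conclusion.** The point holds as a matter of visit order. As written, all 72 active re-doses are given without a routine renal result from later than a few hours after the previous dose, and an effect persisting to Day 8 or 15 would be found only after re-dosing. The 1–4.5 h range is an inference, but the conclusion is the same anywhere within it. It assumes that sites follow the written order; nothing forbids an earlier sample, but nothing requires one.

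The practical size is modest. The likelihood of a delayed, persistent renal effect at weekly doses of 80–120 mg/kg cannot be estimated from these documents and is probably low. The case for change rests on the low cost of closing the gap for the toxicity that the Protocol itself ranks first.

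**What to change.** 1. In *Auditory remediation visits*: on Days 8 and 15, run a urine dipstick for protein and glucose on arrival and read it before the dose. A 2+ protein or unexplained 2+ glucose reading triggers the existing hold. A new 1+ is repeated on a fresh sample before that day's dose: if it has cleared, dose and record the adverse event; if it is still present, hold, as the current rule already says for a positive repeat.

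2. In *Criteria for Early Discontinuation*: state that any repeat prompted by an abnormal result, including 1+ protein or glucose, is obtained and read before the next weekly dose, using the Follow-up visit in Table 1 if needed.

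Keep all post-dose samples.

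**Cost.** 45 × 2 = 90 strips at existing visits and a few sentences of text, with no added routine visit or blood draw. Fecund women already give urine at that point. For cohorts 2 and 3 the change can go into a submission already planned: "After each cohort, we will obtain permission from both the FDA and the IRB via an amendment".

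**Downsides.** If 1–5% of strips are positive by chance (assumed), 90 × 0.01 to 90 × 0.05 gives 0.9–4.5 positives, each of which could delay a session, possibly past the ± 2-day window. A positive glucose strip needs a serum value before it counts as unexplained. Strips do not cover casts or creatinine. The change does not detect effects that clear between visits, and it adds nothing after dose 3.

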Dose escalation plan: *This study has a built-in space between doses, maximizing safety. Furthermore, no side effects were noted in our prior, once weekly intermittent treatment study.* For the present study, potential nephrotoxicity will be monitored through serum chemistry and urine microscopic examination looking for evidence of active sediment (e.g. casts), proteinuria or glycosuria after each dose, as per FDA suggestions. No subjects with baseline renal impairment, as evidenced by a GFR<60 or clinically abnormal laboratories will be enrolled in the study. As attached, FDA has approved our IND, which incorporates the monitoring procedures described above as well as a sequential dose escalation to identify the maximum tolerated dose.

Placebo

The primary risk with placebo is that patients' symptoms may get worse or may not improve. Since patients will remain on their antipsychotic, and the risk of placebo is small.

Potential subjects will be informed about the results of previous studies and will be encouraged to seek treatment outside of the study as an alternative to study participation if they wish.

Antipsychotics:

All subjects will be asked to remain on their pre-study antipsychotics during the study, and any dose changes for this 6 week study, if any, will be included as co-variables for analysis

EEG Recordings

These studies entail the recording of EEG from the scalp employing standard sensors and amplification methods. These procedures are well standardized and there are few known risks. These are principally due to equipment malfunction. The recording equipment used in these studies meet the current design criteria for subject safety, including isolation from potential electrical hazards. Regular preventative maintenance and careful attention to recording procedures further minimize the already insignificant risks of electrophysiological recording. Electrodes and materials used for affixing them in place are kept scrupulously clean and sterilized and materials are utilized which minimize the chance of skin and scalp irritation. Urine pregnancy tests will be conducted at the time of EEG on all female patients to confirm that the patient is not pregnant prior to study drug administration.

Interviews and Neuropsychological Assessments

Interviews and neuropsychological assessments are associated with minimal risk. Some participants may find the interviews and assessments tiring or distressing. Risks are to be minimized by allowing as much flexibility in the interview process (e.g., doing the interview in several meetings, giving breaks) as possible. If subjects have emotional responses, appropriate psychological support is given. Most patients find the interviews and assessments helpful.

Pregnant or Nursing Females

We will not administer experimental medication to pregnant females. For these reasons, pregnant females are excluded from the study. All female patients will demonstrate a negative urine human chorionic gonadotropin (HCG) test prior to sessions to confirm that the patient is not pregnant.

Emergencies

If, during the course of interviewing and assessment procedures, study staff identifies a condition that mandates immediate clinical intervention or official reporting (e.g., homicidality/suicidality), all necessary steps will be taken, and

the emergency procedures of the Division of Experimental Therapeutics, inpatient unit NKI, and the Lieber Clinic will be followed. In the case that staff determine that the participant is at significant risk for self or other destructive behavior, any mental health professional currently treating the participant will be contacted and necessary treatment steps will be taken (e.g., hospitalization, continuous observation, referral to a care provider, etc.). All patients will be given numbers to call in the event of an emergency during treatment: the primary phone number of the treating clinician and the number for the Lieber clinic (both the front desk number and the number for the Doctor- on-call beeper). If the treating clinician, a covering MD in the Lieber clinic, NKI, or the Doctor- on- Call is immediately unavailable, the subject will be instructed to not delay and to go to their nearest Emergency Room.

COVID-19 risks

Going out in public and traveling involves some risk of infection with COVID-19. There is risk of COVID-19 infection during in-office visits and during travel for research purposes.

These risks can be reduced by taking recommended precautions. These include always wearing a mask in public and while traveling, practicing hand hygiene, and staying at least 6 feet away from others. We may be able to arrange alternative transportation for subjects to avoid the subway and the bus.. We have also minimized in-office visits to lessen this risk.

We will keep subjects informed about current public health recommendations, such as federal and local government guidelines and directives.

Methods to Protect Confidentiality

Describe the data management plan and the methods you will employ to protect subject privacy and the confidentiality of research data. The section should detail how information will be collected, recorded, coded, stored, transmitted, and as applicable, shared with other investigators so as to minimize risks related to breach of confidentiality. Confirm that identifiers are removed, to the extent possible, from research data, and explain if there are links between subject identity and research data, or if the data is anonymous. Also, indicate where the data is stored, who is responsible for its safekeeping, and who has access to subject identity and codes, if any, which cross-link research data and subject identity. Confirm that identifiable data is not collected, stored, or transmitted by mail, fax, on removable drives, laptops, or via the internet without proper protections, e.g. encryption.

Describe methods to protect confidentiality

Blood and urine samples, behavioral assessments, EEG recordings, and all other clinical/neuropsychological data will be obtained from the subjects for specific research purposes. Data will include self-report information, observer records, and physiological and behavioral information collected during test sessions. Each subject is assigned a unique ID and all data related to that subject is entered at the site by the site data entry personnel.

Study information will be collected at NYSPI, and entered into a secure electronic database.

For remote visits, we will use HIPAA-compliant videoconferencing, phone and web-based platforms.

Direct Benefits to Subjects

Describe only benefits to individual subjects that are likely to accrue during the study itself. Do not include subject compensation or treatment to be provided at the end of the study, as these do not figure into the IRB's risk benefit

considerations. Do not describe diagnostic and evaluation components unless subjects receive clinical feedback. Do not describe the anticipated scientific benefits of the research. Some studies offer no direct benefit to subjects.

This study was not designed to benefit individual subjects; however, it is possible that some patients might receive some temporary improvement in their symptoms during this study.

References

See main protocol
